To determine the effect of patient race in moderating the effect of 12 months of exposure to CHAMPION on the clozapine prescribing practices of prescribers and objectively measured medication persistence of their patients prescribed clozapine. We will also examine the impact of site and participant characteristics as well as attendance on outcomes.

In summary, if demonstrated to be efficacious, CHAMPION will have significant public impact by increasing the use of clozapine. This project addresses key NIMH priorities including improving access to evidence-based practices, focusing on disparities, and including innovative technologies. This project features a novel intervention, a renowned team of experts and the support of local and national organizations positioned to ensure its success.

PARTICPANTS AND RECRUITMENT AND RETENTION PLAN

Participants and Recruitment and Referral Sources

We will complete all recruitment and enrollment prior to initiation of the intervention. We will enroll 300 prescribers (physicians, nurse practitioners, physician assistants or other doctoral level providers approved to prescribe clozapine in the State of Maryland) as well as other team members at the sites (up to 300). We will recruit prescribers/clinical team from State of Maryland Outpatient Mental Health Centers (OMHC) and other clinical sites. We plan to attempt to enroll approximately 2 OMHCs by county; overall, we plan to enroll approximately 60 sites (approximately 5 prescribers/clinical team per site) with 30 in the CHAMPION group and 30 in the enhanced treatment as usual (TAU) group with N=150 prescribers per group. We may have a few more or less sites to reach the 300 prescriber target for the primary outcome and up to 600 total. We will allow individual prescribers to enroll if they are not affiliated with an enrolled study site, however they will not receive the ANC Point of Care Device, laptop computer, or site stipend. They are eligible for the individual compensation and education benefits if applicable.

Inclusion and Exclusion Criteria

Sites that enroll will have approximately 5 prescribers per site. Other members at the site can enroll. The specific inclusion/exclusion criteria for prescribers includes:

- 1) Located at a site in the State of Maryland with at least 3 prescribers at the site.
- 2) Prescribers/clinical team should be licensed in the State of Maryland and have prescribed antipsychotics previously.

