Our study outcomes are all individual participant outcomes and randomized by sites to ensure we have enough Athelas devices to pass out. We will randomize the individuals by site (N = 60 sites, approximately 3-5 prescribers per site) randomized controlled effectiveness trial to assess if CHAMPION (150 prescribers) significantly increases clozapine prescribing, persistence, knowledge and self-reported competence compared to Enhanced Treatment as Usual (ETAU, N = 30 sites, 150 prescribers). We may have participants from more

CHAMPION PROTOCOL

than 60 sites and more than 300 enrollments to reach the target of 300 prescribers. In addition, individual prescribers signing up will also be randomized to the two conditions. .

We will assess provider level outcomes (knowledge and self-reported competence) immediately before and after the intervention (12 months) and patient level prescribing outcomes (from administrative data) for the year prior to the intervention, during the year of the intervention and for the year following the intervention. This will allow us to estimate the baseline level of clozapine prescribing, the impact during the intervention year and the sustainability of any effects during the year after the intervention is no longer active.

Randomization Procedures

Randomization will occur at the site level for enrolled sites and individual level for prescribers not at enrolled sites. There are NO site outcomes, this randomization allows for the devices to be given to providers in groups to ensure all groups can get a device. The randomization schedule will be created by the study statistician using a randomized block design (block = rural/urban/suburban). We will randomly assign each clinic/prescriber into one of the two study groups using a 1 (CHAMPION) to 1 (ETAU) assignment. Random assignment will occur after agency recruitment and prescriber baseline assessments are completed.

CHAMPION Intervention Condition

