to using a standard Likert scale for self-reported competence evaluation (2). Self-efficacy ratings of competence have been shown to be increased in a mental health ECHO model (6); are recommended as a measure for approaching measurement of practice outcomes (7); and, when using VAS to measure self-efficacy competence, have been found to be a reliable and valid measure for this construct (8-10).

b. Knowledge: We will use multiple-choice questions (MCQ) to assess knowledge. The knowledge-based test questions will consist of 52 questions that will cover 2 questions per 26 topic areas and will conform to best practices and guidelines for design of the questions (11). MCQ have been used to assess knowledge with ECHO models (6, 12) and are known to be a reliable and valid measure for measuring knowledge (11). The total score will range from 0-52 correct answers.

Power

Hypothesis 1: Considering the intent to treat (ITT) approach to analyses, we will be able to assess administrative data prescription records for all prescriber participants regardless of their level of participation in the CHAMPION intervention sessions or other research data collections efforts. Missing data will be a concern only for those time periods where prescriber participants were not practicing in the Maryland public health system (before or after the intervention time period). We assume that we will have administrative data records from at least 85% of the prescribers/clinical team across all time points. We calculated the needed sample size using PASS version 13 (13) for independent proportions in a clustered-randomized design with the following specifications: alpha-level = .05, power = .80, effect size (h) = .39 (small to medium) and ICC = .01 (prescribers/clinical team nested within site). Effect size is based on estimating an 11% improvement in the rate of clozapine prescribing in CHAMPION; e.g. a 4% rate of clozapine prescribing in the ETAU group and a 15% rate in the CHAMPION condition. The required sample size is 254 based on clusters of 4-5 prescribers/clinical team per site.

Hypothesis 2: Even with a conservative estimate of the number of patients per prescriber on clozapine, a high ICC (.20) for patients nested within prescriber, and a small effect (d = .3), the power to detect differences in clozapine persistence between conditions is greater than 95%.

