Hypothesis 3: Although the variables for hypothesis 3 are normally distributed, the specifications are the same and the power calculations are identical to those noted above. Based on literature described in Approach section 10 above, we anticipate changes in knowledge and competence to be large ($>.8$).

Hypothesis 4: Using the values above and the SAS macro from O'Rourke and MacKinnon (14), the power to detect indirect effects (mediation) will be greater than .80 when using the bias corrected bootstrap procedure when paths a and b are at least 0.3 (small to medium effects anticipated).

Statistical Analyses Overview

All data will be screened for errors using frequency and contingency tables and univariate and bivariate plots before formal analysis. These informal plots and summaries will allow us to be cognizant of data distribution characteristics before building regression models. We anticipate that our dependent variables will either have a distribution that is relatively bell-shaped or can be transformed to be relatively bell-shaped. Site will be included in all models as a random effect. Prescriber is nested within intervention arm, by design, and will be specified as a random effect in all analyses that include patient level data. The intercept will be designated as random to account for the non-independence across time point when appropriate. SAS PROC MIXED or GLIMIX will be used for the analyses described below (15).

CHAMPION PROTOCOL

Missing Data

All analyses will be conducted within an ITT framework. As described above, missing data for hypotheses 1 and 2 will be limited due to the use of Medicaid prescription records for those outcomes. For hypotheses 3 and 4, we will compare the baseline characteristics of the prescribers/clinical team who drop out prior to completing the 12-month assessment to those prescribers/clinical team who do complete the assessment. If necessary, we will investigate how estimates/results change over a range of several plausible assumptions regarding the missing mechanism together with multiple imputations to most accurately capture existent random variability.

Multiple Comparisons

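### Randomisation is blocked on rural/urban/suburban location, but no H1–H4 model includes that factor; the likely cost is a slightly conservative H1 test, not an invalid one

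*Combined protocol and SAP*

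**What the plan says.** Under Randomization Procedures, the statistician prepares a 1:1 schedule "using a randomized block design (block = rural/urban/suburban"). Sites are the unit for enrolled clinics. Overview of the Study Design adds "In addition, individual prescribers signing up will also be randomized to the two conditions" and describes sites with "approximately 3-5 prescribers per site".

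The analysis sections name these terms:

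- **Statistical Analyses Overview:** a random site effect in every model, and a random prescriber effect where patient-level data are used.
- **H1:** group, time, group-by-time, control for baseline and random site, tested by a two-sided contrast at t=3.
- **H2:** random site and random prescriber, with the longitudinal part as in H1.
- **H3:** group, control for baseline and random site.
- **H4:** group, the 12-month competence score as mediator, and control for baseline.
- **Multiple Comparisons:** adjustment for site versus individual randomisation.

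Location is in none of them. The nearest text is exploratory: "We will also examine the impact of site and participant characteristics as well as attendance on outcomes" (Exploratory Aims), with a similar general remark under Exploratory Analyses. Neither names location or forms part of the H1–H4 tests.

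**The concern.** Blocking on location makes the arms similar in location mix, so differences between locations largely drop out of the arm comparison. A model with a random site effect and no location term still counts those differences as between-site noise. Its standard error is then a little too large, the test rejects a little too rarely, and some of the precision gained by blocking is lost.

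The plan already carries one feature of the randomisation, site versus individual, into the analysis. The blocking factor itself is left out, which leaves adjustment for it as a choice that could be made after the results are seen.

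**Working it through.** **Inputs from Power, Hypothesis 1.** Two-sided alpha .05, power .80, h = .39, "ICC = .01 (prescribers/clinical team nested within site"), at least 85% data availability, and "The required sample size is 254 based on clusters of 4-5 prescribers/clinical team per site".

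**Assumptions not in the documents.** R² is the share of between-site variance explained by location, taken as 100% (upper bound), 30% and 0. The baseline-to-t=3 correlation r within site is .3, .5 or .7. Arms are balanced within blocks. Outcomes are treated as continuous (linear normal approximation).

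**The plan's own figure.** n per arm = 2 × ((1.960 + 0.842)/0.39)² = 103.2, or 206.4 in total. Multiplying by the design effect 1 + (m − 1)(.01) and dividing by 0.85 gives 250.1 at m = 4 and 252.6 at m = 5. Rounding up per arm at m = 5 gives 2 × 127 = 254. The stated number is reproduced if it already allows for the 85%.

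**Method.** Let s be the share of the variance used by the unadjusted test that is really location variance, and k = √(1 − s). With planned power fixed at 80%:

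- type I error of the unadjusted test = 2(1 − Φ(1.96/k))
- unadjusted power = Φ(0.842/k)
- power with location in the model = Φ(2.802/k − 1.96)

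**Reading 1: t=3 comparison before baseline adjustment.** s = R² × m × .01/(1 + (m − 1)(.01)).

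| m | s at R² = 100% | Type I error | Power without / with location | Loss (points) |
|---|---|---|---|---|
| 1 (individual) | .0100 | 4.89% | 80.1 / 80.4% | 0.3 |
| 3 | .0294 | 4.67% | 80.4 / 81.2% | 0.8 |
| 4 | .0388 | 4.56% | 80.5 / 81.5% | 1.1 |
| 5 | .0481 | 4.46% | 80.6 / 81.9% | 1.3 |

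At R² = 30% and 4–5 per site, the loss is 0.3–0.4 point.

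**Reading 2: baseline as a covariate, stable location effect.** V = .01 + .99/m, C = .01 + r(.99)/m, slope b = C/V. Location variance left is (1 − b)² × R² × .01; residual variance is V − C²/V. Example at m = 5, r = .3, R² = 100%: V = .208, C = .0694, b = .334, residual variance .1848, s = .024, power 80.3 versus 80.9%, loss 0.66 point.

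| m | r = .3 | r = .5 | r = .7 |
|---|---|---|---|
| 4 | 0.54 | 0.34 | 0.18 |
| 4.5 | 0.60 | 0.37 | 0.20 |
| 5 | 0.66 | 0.41 | 0.22 |

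At R² = 30% the loss is at most 0.2 point.

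**Reading 3: t=3 versus t=1 contrast.** A stable location effect cancels, so the loss is zero. If location acts only at t=3, s = R²(.01)/(R²(.01) + 2(1 − r)(.99)/m). Example at m = 5, r = .7, R² = 100%: s = .01/(.01 + .1188) = .0776, power 81.0 versus 83.1%, loss 2.12 points.

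| m | r = .3 | r = .5 | r = .7 |
|---|---|---|---|
| 4 | 0.77 | 1.06 | 1.72 |
| 4.5 | 0.86 | 1.19 | 1.92 |
| 5 | 0.95 | 1.32 | 2.12 |

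At R² = 30% the largest value is 0.68. Here a block main effect alone recovers nothing, because it cancels in the difference; block-by-time is needed.

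**Simulation** (60 sites, 10 per arm in each of three blocks, r = .5, R² = 100%). For Reading 2, power was 79.4% without and 79.8% with location. For Reading 3 with location only at t=3, power was 81.3 versus 82.5% and type I error 4.4 versus 5.0%. With R² = 0, power differed by 0.1 point or less.

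**Other hypotheses.** For H3, "we anticipate changes in knowledge and competence to be large" (above .8). At d = .8, n = 254 and design effect 1.035, power = Φ(.8 × √(254/4/1.035) − 1.96) = Φ(4.31) > 99.9%, so the loss is negligible. For H2 the plan says "Even with a conservative estimate of the number of patients per prescriber on clozapine, a high ICC (.20) for patients nested within prescriber" but does not give the number of patients, so no loss was computed. None was computed for H4.

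**The case against.** The strongest reply is that the effect is too small to matter. H1 controls for baseline, which absorbs much or all of a stable location effect. The larger losses need an effect that appears only at t=3, which nothing in the documents suggests. R² = 100% is also extreme for a three-level factor. All of this stands, and it keeps the point minor.

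The calculations are also linear, while H1 is planned as a log-link mixed model with planning rates of 4% and 15%. Actual block sizes are not given, and sites are mixed with single prescribers. This stands too: the figures are approximations.

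It may be said that the random site effect already covers location. It does not. It treats location differences as noise, which is why the test is conservative. The exploratory look at site characteristics does not change the H1–H4 tests.

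A reader might infer three stronger things:

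- **That the omission inflates type I error or undermines the result.** Under near balance within blocks, the error goes the other way.
- **That 1.1–1.3 points is a ceiling at the planned ICC.** It belongs to a comparison without the baseline control that H1 specifies; Reading 3 reaches 2.1.
- **That power is known to be lost.** The documents report no outcome by location.

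**Conclusion.** The omission is real and minor. The plan randomises within location blocks and does not say that the analysis will follow them.

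For H1 at ICC .01, with 4–5 prescribers per site and location explaining all between-site variance, the loss is about 0.2–0.7 point with baseline as a covariate. With a t=3 versus t=1 contrast it is zero for a stable effect and about 0.8–2.1 points for one acting only at t=3. If location explains 30% of site variance, no reading exceeds about 0.7 point; if it explains none, nothing is lost. The plan does not say which form of baseline control it intends, so one figure cannot be singled out.

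These sizes rest on the planned ICC, balance within blocks and the linear approximation. With a larger ICC, all of it due to location, the loss before baseline adjustment would be 2.1–2.5 points at .02 and 4.6–5.5 at .05.

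**What to change.** State that the rural/urban/suburban block enters the H1–H3 models as a fixed effect alongside the planned site/individual indicator, with block-by-time in the longitudinal H1 and H2 models (and in H3 if it is analysed as repeated measures). For consistency, include the block in the H4 mediator and outcome models. The same edit can say which form of baseline control H1 uses.

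The section on HMIS data reports that Medicaid data have already been obtained. The change should therefore be dated and documented as made before any comparison of outcomes by arm. If such a comparison has already been made, that should be stated.

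The cost is two degrees of freedom for block and four for block-by-time in the three-period models (two in a repeated-measures H3). No new data are needed, since location had to be known to build the schedule. If location proves irrelevant, the simulated power cost is 0.1 point or less under the linear approximation; it was not checked for the log-link model.

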In a randomized controlled design with 26 biweekly sessions over 12 months, we were funded by the National Institute of Mental Health (NIMH) to test the effectiveness of an ECHO-based intervention for improving the use of clozapine in people with treatment-resistant schizophrenia. This intervention, [Clozapine CHAMPION-ECHO \(Center for Help and Assistance for Maryland Prescribers- Improving Outcomes Network using Extension for Community Healthcare Outcomes](#), is referred to as “CHAMPION.” We are measuring antipsychotic prescribing before, during and after the intervention period as the primary study outcome. Statewide Medicaid data from Maryland is the prime source of prescribing data for this study.

We completed recruitment of study sites/prescribers/clinicians in 2021 and included approximately 278 prescribers. The intervention concluded in August of 2022. We have an existing Data Use Agreement for the Medicaid data component with the Hilltop Institute and MDH and that data collection is progressing as planned.

We included clinics and hospitals from around the State of Maryland, and staff and prescribers from State of Maryland inpatient psychiatric facilities also participated. Inpatient prescribing data are not contained in Maryland Medicaid prescription data. **Therefore, we must obtain inpatient prescribing records for antipsychotics (not protected health information) from the state hospital facilities via the Hospital Management Information System (HMIS).**

SCOPE OF DATA:

Time Period:

We are requesting hospital prescription records of antipsychotic prescribing from HMIS and Eastern Shore Hospital (outside HMIS) for the dates of January 1, 2020 to July 31, 2023. This will enable us to examine prescribing patterns during three time periods:

Pre-intervention period: January 1, 2020-July 31, 2021

Intervention period: August 1, 2021 – July 31, 2022

Post-intervention period: August 1, 2022 – July 31, 2023

Variables and Acquisition:

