Analysis of Secondary and Exploratory aims.														
Archive ECHO lectures for website at end of 12 months														
Period of Medicaid Data Collection 2 (Aim 1)														
Post Testing on Knowledge and Self-Reported Competence (Aim 2)														
Meetings with NASHMPD														
Analysis of Project ECHO Post data														
Make videotaped ECHOs available to all participants once 12-month Medicaid data completed.														
National Webinar with NASHMPD and APA CSS SMI														
Submit symposium abstract to national														

CHAMPION PROTOCOL

meetings, e.g. IPS, SIRS														
Data Repository Submission														

STATISTICAL DESIGN AND POWER

Primary Outcomes

Specific Aim 1: The primary outcome examines Maryland Medicaid (and HMIS for inpatient) prescription data, which will be used to assess the increase in the proportion of patients treated with clozapine for those in the care of prescribers/clinical team randomized to the CHAMPION relative to the ETAU condition. We will also examine persistence in the use of clozapine for patients who are prescribed clozapine under the care of prescribers/clinical team randomized to CHAMPION compared to prescribers/clinical team randomized to the ETAU. The specific outcome assessments using Medicaid data include:

a. Proportion of clozapine prescriptions: Clozapine prescribing rates will be calculated from Medicaid prescription data. National Prescriber Identification (NPI) numbers will be used to identify the antipsychotic prescription records for each prescriber in the study. The denominator will be the number of unique individuals with a diagnosis of schizophrenia who had at least 1 prescription for an antipsychotic during each time period (12 months prior to start of study, during active study participation, and 12 months after the intervention period ends). For each individual in the sample, an indicator will be created that reflects whether the person had any prescription for clozapine during each of the time periods.

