b. Persistence to clozapine: Incident episodes of clozapine prescriptions will be identified by a 90 day look back period to identify a new episode of care. Persistence will be measured as the duration of the clozapine episode (in days) from the date of the first prescription record until the first gap of more than 45 days between prescriptions. Prescribing gaps will be calculated by first adding the days' supply to the dispensing date of each prescription to identify the date the prescription should be exhausted. Days that the patient is hospitalized will not be included in the calculation of episode duration. The first gap in prescribing of 46 days or more will be considered a discontinuation of the medication. An episode will only be right censored at the study endpoint, otherwise an episode can continue into the next time period. If a person has more than 1 episode of clozapine use during any time period, we will select the first episode.

Specific Aim 2: We will measure two educational outcomes: self-reported competence of prescribers/clinical team in using clozapine and knowledge associated with clozapine treatment. These will both be measured before and after the 12-month intervention period. These outcomes have been selected, because they are measurable and pilot data has already established that prescribers/clinical team will rate competence and answer questions on clozapine knowledge. In addition, we will pilot-test all questions and review the self-reported competence measure prior to the administration of the CHAMPION intervention.

a. Competence: Our measurement of competence will be based upon self-report assessment guided by Bandura's theory of self-efficacy (2, 3) and we are using a definition of competence as "the perceived self-efficacy rating of one's judgment to use clozapine"(2, 4). We will use a Visual Analog Scale (VAS) (0-100 mm) will serve as the primary outcome. Self-reported competence ratings will be evaluated for the overall use of clozapine and for each of the CHAMPION session topic areas. The VAS format has been found to be superior

CHAMPION PROTOCOL

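### The persistence rule removes hospital days from episode length but, as written, not from the 46-day gap or the 90-day look-back, so a long stay on clozapine can read as a discontinuation or a new start

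*Combined protocol and SAP*

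**What the plan says.** The rule is in the combined protocol and SAP, Primary Outcomes, item b (Persistence to clozapine). Its parts are:

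- New episode: "Incident episodes of clozapine prescriptions will be identified by a 90 day look back period to identify a new episode of care".
- Gap: "Prescribing gaps will be calculated by first adding the days' supply to the dispensing date of each prescription", which gives the run-out date.
- Hospital days: "Days that the patient is hospitalized will not be included in the calculation of episode duration".
- End of episode: "The first gap in prescribing of 46 days or more will be considered a discontinuation of the medication".
- Censoring: "An episode will only be right censored at the study endpoint, otherwise an episode can continue into the next time period".
- Repeat episodes: "If a person has more than 1 episode of clozapine use during any time period, we will select the first episode".

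Hospital days appear once, for duration. The look-back, gap, discontinuation and censoring rules do not mention them.

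On data sources, HMIS Data and Security says "Inpatient prescribing data are not contained in Maryland Medicaid prescription data". It adds that prescribers from state inpatient facilities took part, which is why hospital records are being requested. The opening of Primary Outcomes says "The primary outcome examines Maryland Medicaid (and HMIS for inpatient) prescription data", in the sentence about the proportion treated with clozapine. It then introduces both outcomes as based on Medicaid data, and Hypothesis 2 is worded as assessed from Medicaid prescriptions. No section says whether hospital orders count towards persistence.

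**The concern.** Days of clozapine use are the Hypothesis 2 outcome, and the first long gap fixes where the count stops. A patient who takes clozapine throughout an admission generates no Medicaid fill during it. Unless the gap calculation discounts those days, the admission looks the same as stopping the drug: the episode is closed at the last run-out date and all later use is lost from it. The same blank interval can make the first fill after discharge look like a new start.

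The error therefore falls on the outcome itself and on who enters the analysis. Allocation is mainly by site and is blocked on rural, urban or suburban location, so the design does not specifically balance exposure to long inpatient stays.

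**Working it through.** **The plan's own figures.** The plan gives no figure for hospital stays. Its only figure for Hypothesis 2 is power above 95%, which is not disputed here. With 150 prescribers per arm, d = 0.3, ICC = 0.20, two-sided alpha of 0.05 (stated for Hypothesis 1, assumed here) and effective n = 150m / (1 + (m − 1) × 0.20), power is 91.8% for m = 2 clozapine patients per prescriber and 96.7% for m = 3. The plan does not state m, so the figure can be neither confirmed nor refuted.

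**Inputs.** From item b: gap = next fill date − (last fill date + days' supply), discontinuation at 46 days or more, look-back of 90 days. Assumed: days' supply S of 7, 14, 28 or 30, and a refill on the day of discharge unless stated. Let a be the days from last fill to admission (0 to S − 1) and L the length of stay. Only Medicaid fills are counted.

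**One patient.** A 30-day fill on day 0, admission on day 10, a 90-day stay on clozapine ending on day 100, next fill on day 101.

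- Gap as written: 101 − 30 = 71 days, which is 46 or more, so coded as discontinued on day 30.
- Hospital days within the gap: 100 − 30 = 70. Removing them leaves 1 day (0 if the discharge day counts as a hospital day), so the episode continues.
- Look-back: 101 days since the last fill (a new start if counted from fill date), but 71 days since run-out (not new if counted from run-out). The plan does not say which count applies.

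**Shortest stay that triggers each error.**

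- Gap: a + L − S ≥ 46, so L ≥ S + 46 − a.
- Look-back from fill date: a + L > 90, so L ≥ 91 − a.
- Look-back from run-out: a + L − S > 90, so L ≥ S + 91 − a.

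| Days' supply | Coded as stopped | New start, from fill date | New start, from run-out |
|---|---|---|---|
| 7 | 47–53 | 85–91 | 92–98 |
| 14 | 47–60 | 78–91 | 92–105 |
| 28 | 47–74 | 64–91 | 92–119 |
| 30 | 47–76 | 62–91 | 92–121 |

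Each range is the threshold in days of stay. The low end is a patient with least supply left at admission, the high end one admitted on the day of a fill.

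**Effect on the outcome.** Take continuous use for 365 days, 30-day fills on days 0, 30, 60 and 90, and admission on day 100. Supply runs out on day 120, so the gap is (100 + L) − 120. If the gap is 46 or more, the rule as written closes the episode on day 120 and removes 20 hospital days: 120 − 20 = 100. With hospital days also removed from the gap, there is one episode of 365 − L days.

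| Stay (days) | Gap as written | Days counted as written | Days counted, gap adjusted |
|---|---|---|---|
| 65 | 45 | 300 | 300 |
| 66 | 46 | 100 | 299 |
| 80 | 60 | 100 | 285 |
| 120 | 100 | 100 | 245 |

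**Wholly inpatient episode.** If a hospital order could open an episode and the patient stayed in hospital throughout, every day would be removed from duration and the count would be 0.

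**The case against.** The strongest reply is that the authors may have meant hospital days to come out of the gap as well. The sentence sits between the gap formula and the discontinuation rule, and the gap determines the duration. That reading is possible, but the text does not state it. Two programmers could follow item b and produce different outcomes for the same patient.

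A second reply is that linked HMIS orders could bridge both the gap and the look-back. That holds only if such orders count for Hypothesis 2, which the plan does not say, and only for stays covered by those records.

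Three stronger readings are tempting, and the documents do not support them.

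- *Every long stay counts as stopping, and every discharged patient as a new start.* Only stays beyond the thresholds above do so, and only where no inpatient record fills the interval. If the earlier episode began in the same study period, the first-episode rule drops the restart. A false start enters when it falls in a different period, or when a patient first started in hospital is dated from the first community fill.
- *State-hospital patients contribute no days.* Patients discharged on clozapine contribute their community days. A count of 0 for wholly inpatient patients presupposes that HMIS orders open Hypothesis 2 episodes, whereas the gap and look-back errors presuppose that inpatient orders do not count. If HMIS is outside Hypothesis 2, those patients have no episode at all.
- *The comparison of arms is biased.* The rule is the same in both arms. CHAMPION might change inpatient starts, but no figure in the documents supports a direction or a size.

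**Conclusion.** The point holds as a defect in a stated rule. Followed literally on Medicaid fills, it codes a continuing clozapine user as discontinued once a stay reaches 47 to 76 days (30-day fills). It can code the same patient as a new start once the stay reaches 62 to 121 days, depending on supply at admission and on how the look-back is counted. For an affected patient the error is large: 100 days against 285 in the 80-day example. Stays below the thresholds are unaffected.

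These figures rest on assumed days' supply, a refill at discharge, and no inpatient order bridging the interval. The documents give no admission rate or length of stay, so the number of affected patients and any difference between arms cannot be computed. The rule should be settled before the persistence data are analysed.

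**What to change.** 1. Subtract hospital days from the gap and look-back counts as well as from duration, using inpatient claims and HMIS admission and discharge dates. State whether the look-back runs from fill date or run-out date, and how a patient still in hospital at the study endpoint is censored.
2. Where a patient links by Medicaid ID, treat HMIS clozapine orders as prescription records for the look-back.
3. State whether HMIS orders can open a Hypothesis 2 episode. If they cannot, say that wholly inpatient patients are outside Hypothesis 2. If they can, do not also remove those patients' hospital days from duration, because a wholly inpatient episode would then count 0 days.
4. Report the number of stays and orders that could not be linked, and give the result under the rule as written as a sensitivity analysis.

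The cost is specification and programming on data already requested. The main limit is linkage: HMIS supplies a Medicaid ID only where applicable, the Eastern Shore column lists none, the Gladstone data are de-identified, and inpatient claims are listed only for a 295 diagnosis. Claims can show a stay but not clozapine use during it, so a patient taken off clozapine in hospital and restarted soon after discharge would be counted as continuing.
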